4.4 Premature Termination Of Study/Closure Of Center

The sponsor has the right to close this study at any time, although this should occur only after consultation between involved parties. The Ethics Committee/Institutional Review Board (EC/IRB) must be informed. Should the study/center be closed prematurely, all study materials (except documentation that has to remain stored at site) will be retained on site by the sponsor/investigator.

4.5 Treatments**4.5.1 Treatments To Be Administered**

This study is designed with two blinded treatment groups (C1INH vs. Placebo). Each group will include 20 patients in a treatment arm and 20 patients in a placebo arm.

This design is not statistically powered to show significant differences if there is a 30-50% reduction in the treatment group but may trend towards positive treatment effect since extensive DGF (40-50%) is expected in KDPI >80 recipients. The dose of C1INH chosen is (500U/kidney) which should be sufficient to bind all endothelial surfaces in the transplanted kidney. This is based on our observations from our experience using C1INH vs. placebo to prevent antibody-mediated rejection in humans. In those randomized to placebo, an equivalent volume of placebo (0.9% normal saline) will be administered prior to graft reperfusion. Both groups (C1INH or placebo) will receive an intrarenal administration of heparinized normal saline before study drug administration.

Patients who fulfill all I/E criteria will be eligible to be enrolled into this Phase I/II study.

4.5.2 Identity Of Investigational Product(s)

Medication will be labeled according to the requirements of local law and legislation. Label text will be approved according to agreed CSMC Research Pharmacy procedures.

Product name: Berinert® / C1INH (Human)

Chemical name: Complement Factor 1 Inhibitor (C1INH)

Study Medication & Dosing: Berinert® is available in a single-use vial that contains 500 units of C1 esterase inhibitor as a lyophilized concentrate. Each vial must be reconstituted with 10 mL of diluent (sterile water) provided. Prior to reconstitution, Berinert® should be stored at 2° to 25°C. After reconstitution, administration may begin within 8 hours provided the solution has been stored at up to 25°C. Berinert® is dosed as a 500U/kidney infusion 1-2 hours prior to implantation of the KDPI >80 kidney. Participating patients will receive 500U/kidney C1 INH vs placebo (0.9% NS) prior to implantation, (see Appendix A). The C1INH or placebo dose will be preceded by an intrarenal administration of heparinized normal saline.

4.5.3 Method Of Assigning Subjects To Treatment Groups

Patients will be randomized into treatment/placebo arms in a 1:1 ratio. Randomization will be completed prior to patient entering the operating room for transplantation.

This study is a double-blind, placebo-controlled study. The clinical pharmacist will maintain the randomization assignment. The Investigators, other study personnel, patients, and the Sponsor will be blinded to treatment assignment.

4.5.4 Selection Of Doses In The Study**4.5.4.1 Berinert® (C1INH Dosing)**

For the planned study, subjects will receive C1NH 500U/kidney infused into the renal artery pre-operatively 1-2 hours before graft reperfusion. For all dose reconstitutions, Berinert® is provided in single dose vials of 500 units. Each vial will be reconstituted in 10 ml sterile water for injection. Placebo will be administered in an identical volume. C1INH will be preceded by an intrarenal administration of heparinized normal saline prior to renal vein anastomosis.

4.5.4.2 Placebo Dosing

The placebo used in this study will be 0.9% normal saline administered as a single dose into the renal artery, 1-2 hours before graft reperfusion. The total volume will be identical to that calculated for Berinert® infusions. Placebo will be preceded by an intrarenal administration of heparinized normal saline prior to renal vein anastomosis.

4.5.5 Immunosuppression

Immunosuppression regimen is an important part of the care for recipients of kidney transplantation. The regimen to be used in this study is reflecting the fact that the patients enrolled into this study are at high risk for developing poor or delayed graft function.

4.5.5.1 Induction Antibody Therapy

All patients enrolled into this study will be treated with induction antibody therapy with Thymoglobulin® OR Campath 1H. For Thymoglobulin®, the first dose will be given immediately after the transplantation procedure to follow with additional doses so that patients receive up to 6 mg/kg (1.5mg/kg/dose) using standard institutional treatment guidelines for use of this agent in this patient population. Campath 1H will be administered in a single 30 mg subcutaneous dose post-transplant. No induction administration of IL-2 receptor inhibitors is permitted in this protocol.

4.5.5.2 Maintenance Immunosuppression**4.5.5.2.1 Calcineurin Inhibitors (Tacrolimus or Cyclosporine)**

Tacrolimus (Prograf) and Cyclosporine (Neoral) are indicated for the prophylaxis of organ rejection in patients receiving allogeneic kidney transplants. Tacrolimus or Cyclosporine will be initiated and monitored with trough levels using standard institutional treatment guidelines for use of these agents in this patient population. If conversion to belatacept is deemed necessary per SOC process, this is allowable during study participation

4.5.5.2.2 Mycophenolate Mofetil (MMF)

Mycophenolate mofetil (MMF, CellCept), the morpholinoethylester of mycophenolic acid, has been shown to have antiproliferative effects on lymphocytes by blocking proliferation of T- and B-lymphocytes. MMF will be dosed using standard institutional treatment guidelines for use of these agents in this patient population. Myfortic can be used instead of CellCept and will be dosed using standard institutional treatment guidelines for use of these agents in this patient population.

4.5.5.2.3 Corticosteroids

Corticosteroids will be administered using standard institutional treatment guidelines for use of these agents in this patient population.

4.5.6 Anti-infective Prophylaxis

Valgancyclovir for the prophylaxis of CMV infection will be used for a minimum of 6 months. If PO administration of valgancyclovir is not possible, the use of ganciclovir while the patient is inpatient is also permissible.

Local standards of care for post-transplant bacterial and fungal prophylaxis will be applied using standard institutional treatment guidelines for use of these agents in this patient population.

4.5.7 Selection And Timing Of Dose For Each Subject

The active treatment arm (Berinert® 500U/kidney) will be compared to a placebo control treatment arm, with a total of 20 adult subjects in each study group. A total of 40 adult subjects will be enrolled in the study and additional subjects will not be enrolled to replace dropouts. This design is not statistically powered to show differences in DGF; a 30-50% reduction in DGF predicted for the Berinert® study group. Treatment effect will be investigated following renal artery infusion with Berinert® or an equivalent volume of placebo (0.9% normal saline) pre-operatively prior to graft reperfusion. The C1INH or placebo dose will be preceded by an intrarenal administration of heparinized normal saline.

If a patient is enrolled into the study but the transplant does not occur as planned (e.g. transplant is cancelled due to donor organ quality at time of transplant), the patient will be considered a "screening without transplant". The patient will be maintained on the study ID # that was assigned

CONFIDENTIAL

C1INH (Berinert®) IRI Study in Kidney Transplant

at enrollment but will not be followed past the screening day. IF the patient receives another transplant offer (at any time while study enrollment is still open), the patient will be allowed to continue with the study protocol, with Day of Transplant = Day 0, as if the screening and consenting occurred during the current admission.

4.5.8 Blinding

The investigational drug pharmacist will be contacted by the study staff and informed of a patient's eligibility. The pharmacist will prepare the blinded study medication or placebo. The study treatment will be prepared according to a pharmacist-supplied randomization code (blinded from all other study personnel). The study treatment will be prepared in a non-siliconized sterile syringe (Berinert® {500U} for all individuals) and labeled with:

- Protocol Number
- Screening number
- Randomization number.

The pharmacist will check the non-siliconized IV syringe for potential particulates. If none are found, the blinded syringe of study treatment, labeled as stated above, will be transported to the surgical suite and matched with the matching patient chart. For the placebo arm, an equivalent volume of normal saline will be prepared in an identical dispensing medium as the C1INH product, labeled as stated above, and transported to the surgical suite and matched with the matching patient chart. Before the study treatment (Berinert or placebo), heparinized normal saline will be administered to the allograft. This method of drug administration has not been FDA approved and may have unforeseen risks

In case of a medical emergency, the study drug assignment for a particular patient may be unblinded. Unblinding study drug assignment will only be necessary if knowledge about treatment is needed for the medical management of the patient. The patient's treatment assignment can be identified for unblinding purposes by calling the Investigational Pharmacist [contact]). When this is necessary, the investigator must immediately notify the IRB, and document the reason and date of the un-blinding. The event must also be documented on the study termination record, the AE page of the CRF, and in source documents. Additionally, the Principal Investigator will submit to the IRB a written explanation describing the event within 5 working days. The procedures for un-blinding study drug treatment will be provided to the Principal Investigators prior to study implementation.

4.5.9 Treatment Compliance

There is only one application of the drug, which takes place approximately 60-120 minutes prior to graft reperfusion administered pre-operatively.

4.6 Study Variables

4.6.1 Efficacy Variables

4.6.1.1 Primary Efficacy Endpoints

For patients who require dialysis in the first 30 days: (Excluding patients who get dialysis for hyperkalemia)

- The proportion of patients enrolled who require at least one session of dialysis in the first 30 days post transplant.
- Number of dialysis sessions per patient in the first 30 days post-transplant.

Renal function and graft survival 6M

- **eGFR at 6M post-transplant**
- **Patient and graft survival at 6M post-transplant**

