- Patients with a history of thrombosis or hypercoagulable state, excluding access clotting.
- Patients with a history of administration of C1INH containing products or recombinant C1INH within 15 days prior to study entry.
- Patients with a known hypersensitivity to treatment with C1INH.
- Patients with an abnormal coagulation function. (INR >2 , PTT > 50 , PLT $<60,000$) who are not on anti-coagulation.

	
6) Patients with known active presence of malignancies.
 
7) Patients who are PCR positive for Hep B, Hep C, or HIV.
 
8) Recipients of pre-emptive kidney transplantation (unless baseline SCr is ≥ 4 mg/dL, making minimal urine output)
 
9) All zero mismatch kidneys.
 
10) Recipients of multi-organ transplants. (kidney and any other organ)
 
11) Recipients of kidney allograft that was arriving on pump preservation
 
12) Recipients of kidney allograft from a living donor.
 
13) Female subjects who are pregnant or lactating.

STUDY ENDPOINTS	
SAFETY:
 
 Overall incidence of adverse events and serious adverse events and relationship of AE and SAEs to the study treatment Need for HD in the 1st month post-transplant. eGFR at 1M, 3M, 6M Patient and graft survival at Day 180 Rate of acute cellular rejection (ACR) and antibody mediated rejection at 6M 
EFFICACY ASSESSMENTS:
 
Primary Endpoints
 
Need for Dialysis in the 1st Month Post-Transplant: (Excluding patients who get dialysis for hyperkalemia)
 
 The proportion of patients enrolled who require at least one session of dialysis in the first 30 days post transplant. Number of dialysis sessions per patient in the first 30 days post transplant. 
Renal Function and Graft Survival 6M
 
 eGFR at 6M post-transplant Patient & Graft survival 6M post-transplant 
Secondary Endpoints
 
 Rate of acute cellular and antibody mediated rejection episodes by day 180 Calculated creatinine clearance at 1M, days 90, 180days post transplant. Development of DSAs at 6M SOC biopsies will be assessed at time of implantation and 6M post implantation.
IMUNOSUPPRESSION REGIMEN	
 Induction therapy using Thymoglobulin in divided doses (total of 6mg/kg) or Campath 1H 30mg SQ x 1. Calcineurin inhibition (Tacrolimus or Cyclosporine) will be initiated as per standard practice

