4.6.4.10 Rate and Duration of Dialysis

Duration of dialysis will be measured by the number of sessions of dialysis treatment needed in the first 30 days post transplant. As for rate of dialysis, one dialysis session will represent the need for dialysis treatment.

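### The primary dialysis endpoint excludes patients by a dialysis indication that arises after randomisation, and section 4.6.1.1 contradicts itself on the denominator

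*Combined protocol and SAP*

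**What the plan says.** The synopsis (section 2.2) heads the first primary efficacy endpoint "Need for Dialysis in the 1st Month Post-Transplant: (Excluding patients who get dialysis for hyperkalemia". Section 4.6.1.1 heads the same endpoint "For patients who require dialysis in the first 30 days: (Excluding patients who get dialysis for hyperkalemia". Both carry the hyperkalemia exclusion, worded at patient level. Only section 4.6.1.1 also restricts to patients who need dialysis.

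Two bullets follow in both places. The first is "The proportion of patients enrolled who require at least one session of dialysis in the first 30 days post transplant". The second is "Number of dialysis sessions per patient in the first 30 days post-transplant", with no denominator stated.

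Other relevant text:
- Section 4.5.3: "Randomization will be completed prior to patient entering the operating room for transplantation".
- Section 4.6.4.10: "As for rate of dialysis, one dialysis session will represent the need for dialysis treatment". It makes no exception for hyperkalemia.
- The synopsis safety list includes need for haemodialysis in the first month, also without the exclusion.
- Section 4.5.7 covers enrolled patients who are not transplanted ("If a patient is enrolled into the study but the transplant does not occur as planned"). They are not followed past screening unless a later offer leads to transplant.
- Section 6.1 is a heading with no text, and the synopsis promises only descriptive and comparative statistics.

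**The concern.** Randomisation precedes surgery, so dialysis in the next 30 days and its indication both arise afterwards. Treatment could affect the indication: a graft that works somewhat better may change why a patient is dialysed, as well as whether. Removing patients on that basis leaves two groups that are no longer the randomised groups. The documents do not say whether such a patient leaves the denominator, counts as not dialysed, or loses only those sessions. Nor do they cover a patient dialysed both for hyperkalemia and for another reason.

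The second problem is the restriction in the 4.6.1.1 heading. If it were applied to the session count, that count would be taken only among patients who already had the outcome. A drug that prevents dialysis changes who is in that group, so the comparison conditions on the outcome.

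First-month dialysis is the first-listed primary efficacy endpoint and the first secondary objective in section 2.1. What is at stake is the efficacy estimate that this pilot would pass on to a later trial.

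**Working it through.** **Inputs.** From the documents: 20 patients per arm (synopsis, section 4.5.7); DGF of 40-50% expected (section 4.5.1); and "a 30-50% reduction in DGF predicted for the Berinert® study group" (section 4.5.7). Assumed: the 40-50% applies to dialysis over 30 days, with midpoint p = 0.45; the share h of dialysed patients whose only indication is hyperkalemia is 10-40%. The documents give no figure for h, and no calculated figure of their own to reproduce.

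**1. The texts side by side.** Applied to the first bullet, the 4.6.1.1 heading gives a proportion of 100% in each arm before the exclusion, because every patient in the denominator would have been dialysed. That cannot be meant. It contradicts the bullet's own denominator and the synopsis heading. The second bullet has no denominator of its own to override the heading. Section 4.6.4.10 counts any one session, so it disagrees with the exclusion.

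**2. One arm under each reading.** Take 9 of 20 dialysed, 2 of them for hyperkalemia only (2/9 = 22%, inside the assumed range).
- Any indication: 9/20 = 45%.
- Patients removed: 7/18 = 38.9%.
- Patients counted as non-events: 7/20 = 35%.

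**3. Equal shares in both arms.** The expected rate is p(1-h)/(1-ph) if patients are removed and p(1-h) if they are non-events. With no true effect both arms get the same value, so the null is not biased. With a true 45% v 27% (risk ratio 0.60):

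| h | Removed | Risk ratio, removed | Risk ratio, non-events |
|---|---|---|---|
| 10% | 0.424 v 0.250 | 0.59 | 0.60 |
| 25% | 0.380 v 0.217 | 0.57 | 0.60 |
| 40% | 0.329 v 0.182 | 0.55 | 0.60 |

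**4. Precision.** No true effect, p = 0.45. In each arm, dialysed d ~ Bin(20, 0.45) and hyperkalemia-only k ~ Bin(d, h), enumerated exactly. Probability that the observed risk ratio is at most 0.70 or at least 1/0.70 = 1.43:

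| h | Removed | Non-events |
|---|---|---|
| 0 (no exclusion) | 34.3% | 34.3% |
| 10% | 36.1% | 38.4% |
| 25% | 41.6% | 43.8% |
| 40% | 48.6% | 50.5% |

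This comes from having fewer events. For scale, the no-exclusion figure itself runs from 38.8% at p = 0.40 to 29.1% at p = 0.50.

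**5. Unequal shares, no true effect.** Assume h = 10% on control and 30% on treatment, p = 0.45.
- Removed: 0.405/0.955 = 0.424 v 0.315/0.865 = 0.364, a spurious relative reduction of 14.1% (15.2% at p = 0.40, 13.1% at p = 0.50).
- Non-events: 0.405 v 0.315, a reduction of 1 - 0.70/0.90 = 22.2% at any p.

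With the shares swapped, the result is a spurious increase of 15-18% (removed) or 29% (non-events). In counts: 9/20 v 9/20 with 1 and 3 hyperkalemia patients becomes 8/19 = 42.1% v 6/17 = 35.3% (removed), or 8/20 = 40% v 6/20 = 30% (non-events).

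**6. Sessions, if limited to dialysed patients.** Constructed example: control has 10/20 dialysed, five with 2 sessions and five with 8. The drug prevents 4 of the 10 (40%, the midpoint of the predicted reduction), two of each kind.
- Dialysed only: 50/10 = 5.0 v 30/6 = 5.0.
- All 20: 50/20 = 2.5 v 30/20 = 1.5.

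Over every split of the 4 prevented cases, the treated dialysed-only mean runs from 18/6 = 3.0 to 42/6 = 7.0 against 5.0. The all-patient mean always falls, to between 0.9 and 2.1 against 2.5.

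**The case against.** The 4.6.1.1 heading is most naturally a loose topic label. The first bullet names its own denominator, the synopsis has the same bullets without the restriction, and no section says that sessions will be averaged. Even on the literal reading the proportion is reported too, so in step 6 the 6/20 v 10/20 stays visible. This stands. A reader might infer that the plan analyses sessions among dialysed patients only; the documents do not support that. What remains is a contradiction in wording, and the session count is the bullet it leaves open.

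On the exclusion, a reader might infer that it biases the result. The documents do not show that. Bias needs shares that differ by arm, and the documents give no shares. Double blinding (sections 4.5.3 and 4.5.8) limits differential labelling of the reason for dialysis. This also stands in part, but blinding does not rule out a treatment effect on the indication, nor chance imbalance with 20 per arm.

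Finally, the synopsis safety item already gives an all-cause proportion, safety is the primary objective (section 2.1), and the trial is stated not to be powered for DGF. These limit the consequence. They do not supply the missing counting rule.

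**Conclusion.** The point holds. The exclusion rests on a post-randomisation indication, appears in both statements of the endpoint, and conflicts with the first bullet and with section 4.6.4.10. Nothing in the documents says how to apply it. Separately, the 4.6.1.1 heading is internally contradictory.

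The size depends on hyperkalemia shares that must be assumed. Equal shares cost precision (34.3% rising to 36-51% for shares of 10-40%) and leave the risk ratio nearly or fully unchanged. Shares of 10% v 30% with no true effect and a dialysis rate of 40-50% give a spurious reduction of 13-15% if patients are removed, or 22% if they count as non-events. Those unequal shares illustrate what could happen; they are not a prediction. It would also go too far to infer a false confirmatory claim: an unpowered pilot makes none. The harm is a potentially misleading efficacy estimate. This should be fixed, with high confidence in the conflict of wording and less in any particular amount of bias.

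**What to change.** - **Heading.** In section 4.6.1.1, use the synopsis heading in place of the restriction to dialysed patients, and drop the exclusion in parentheses in both places.
- **Denominator.** In the synopsis and sections 4.6.1.1 and 4.6.4.10, state that all randomised and transplanted patients stay in the denominator of both bullets, by assigned arm. Patients with no session contribute 0. Enrolled patients never transplanted have no post-transplant outcome.
- **Two versions.** Report (i) dialysis for any indication, which matches section 4.6.4.10 and the synopsis safety item, and (ii) a version in which sessions given only for hyperkalemia are not counted. In (ii), a patient with any session for another indication is an event. Fix before unblinding which is primary.
- **Recording.** Record the indication for each session while blinded.
- **Death and graft loss.** State how death or graft loss before day 30 is counted, so that neither is scored as a favourable 0.

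The cost is protocol wording, one recorded item if the dialysis assessment does not already hold it, and one extra analysis. Version (ii) still depends on a post-randomisation judgement and has fewer events; version (i) beside it shows how much that matters. The change concerns counting only, not when to dialyse.

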4.6.1.2 Secondary Efficacy Endpoints

- Calculated Creatinine Clearance obtained at 1M, 3M, 6M post-transplant.
- Rate of acute cellular and antibody mediated rejection episodes by day 180
- Development of DSAs at 6M
- Analysis of renal transplant biopsies at time of implantation and at 6M as clinically indicated.

4.6.2 Safety Variables

4.6.2.1 Adverse Drug Reactions: The most serious adverse reaction reported in subjects in clinical studies who received Berinert® was an increase in the severity of pain associated with hereditary angioedema. In a placebo controlled clinical study, the incidence of adverse events occurring in more than 4% of subjects (n = 43) receiving Berinert® up to 72 hours after infusion was nausea (7%), headache (7%), abdominal pain (7%), dysgeusia (4.7%), vomiting (2.3%), pain (2.3%), and muscle spasms (2.3%). Adverse reactions can persist 7-9 days after infusion and have been reported to be abdominal pain (6.5%), diarrhea (4.6%), nausea (6.5%), vomiting (4.6%), headache (11.1%), hereditary angioedema recurrence (11.1%), muscle spasm (5.6%), and pain (5.6%). Subjects were tested at baseline and after 3 months for exposure to parvovirus B19, HBV, HCV, and HIV-1 and HIV-2. No subject who underwent testing evidenced seroconversion or treatment-emergent positive polymerase chain reaction testing for the above pathogens. Post-marketing reports from Europe since 1979 in patients receiving Berinert® for treatment of HAE include hypersensitivity/anaphylactic reactions, a few suspected cases of viral transmission, including cases of acute hepatitis C, injection-site pain, injection-site redness, chills, and fever. See Novation Drug Monograph for Berinert®. Berinert® was well tolerated with minimal AE/SAE profile in our kidney transplant studies (Appendix B).

4.6.2.2 Assessment of Risk for Thrombotic Events with C1INH Administration: Patients with known risk factors for thrombotic events will be monitored for signs and symptoms of thrombosis, such as new onset swelling and pain in the

limbs or abdomen, new onset chest pain, shortness of breath, loss of sensation or motor power, or altered consciousness, vision, or speech. Patients will be assessed for evidence of DVT or other TEs per the usual standard process. Routine measurements of coagulation factors to evaluate DIC (D-Dimers, fibrinogen, PT, PTT) will be performed per standard process.

4.6.2.3 Evidence of a Thrombotic Effect of C1INH Administration when Given in Supraphysiologic Dosages to Humans: The German Medical Profession's Drugs Committee (AkdÅ) reported on 13 cases of severe thrombus formation after Berinert® infusions. These infusions were given to neonates undergoing cardiac surgery and doses of Berinert® were given at exceedingly high doses (~500U/kg) without control studies (see Appendix C). Nine of these infants died of this complication. The conclusions from this report are as follows:

- There are no studies to support the use of C1INH outside of those with hereditary angioneurotic edema.
- The use of C1INH in patients who do not have C1INH deficiency may result in abnormal coagulation parameters with propensity to thrombosis.
- There are no controlled studies that suggests a benefit of C1INH therapy in conditions other than C1INH deficiency.
- Any proposed uses outside of C1INH deficiency should be conducted in a controlled manner to monitor for unexpected or unanticipated side effects of C1INH therapy.

Clearly, this is a serious and unanticipated complication of C1INH therapy that could potentially limit its use in patients with other conditions where complement inhibition would be desirable. This is the case with our proposal. Inhibition of complement activation post-transplant has great potential for prevention of complement-dependent DGF. In addition, there is an important unmet need for new therapeutics in the prevention and treatment of DGF. Despite this, it is important to assess the tolerability and safety of C1INH therapy in this patient population. Although the C1INH dosing proposed in our study is much less than that reported to be associated with TE and well below therapeutic dosing recommendations (20-50U/kg) (500U/kidney once on Day 0), and will be administered intra-renally, there is still a possibility that increasing C1INH levels above normal baseline could have deleterious effects and induce coagulation abnormalities. Recent safety data from clinical trials of C1INH for use in C1INH deficiency have not reported TE with one exception of a basilar artery thrombosis in a patient treated for C1INH deficiency (Appendix C). This event was deemed unrelated to C1INH therapy. As previously indicated if significant coagulation abnormalities or TE events are seen in any study patient, the study will be terminated. However, data from our recently completed study of C1INH in prevention of antibody-mediated rejection (NCT01134510) in a randomized placebo controlled study showed no evidence of thrombotic events in any patient treated with Berinert® at 20U/kg x 8 doses given during the first month post-transplant. In addition, recent reports from the FDA (Gandhi et al) suggests that thrombotic events do occur with C1INH therapy, but most cases are associated with the product (Cinryze®).

4.6.2.4 Evidence of a Thrombotic Effect of C1INH Administration when Given in Supra-physiologic Dosages to Animals: Data on C1INH transgenic mice show that blood levels as high as 2mg/ml (NL 25 µg/ml) are produced without reported effects (34) (Appendix D). Other investigators have shown that ischemia-reperfusion injury is reduced in animals transgenic for C1INH expression (Appendix D). Data provided by CSL Behring (Appendix D) shows that administration of Berinert® up to 200U/kg daily for 14 days had no deleterious effects and did not induce coagulation abnormalities.

